6.2 MANUFACTURING AND ADJUSTABILITY

The "Quick Clip" mechanisms from the Ponseti SBs are manufactured by MD Orthopaedics in Wayland, Massachusetts (17). The DB prototypes are mainly manufactured in-house by SickKids using 3D printing, however the machining of the L-components is outsourced to Sunnybrook Hospital. The DB will be preassembled and given to the participants ready-to-use.

The new DB can be adjusted via bolts and set screws, so that the feet are kept at specified abduction angles and shoulder-width distance apart. At the time of intervention, the DB will be sized to each patient by a clubfoot provider. The parent will also be educated on how to adjust the sizing of the bar should they need to.

6.3 MEASURES TO MINIMIZE BIAS: RANDOMIZATION AND BLINDING

Each patient will be assigned a unique study ID. Patients will be assigned to an arm by drawing lots. This will be done by preparing 20 opaque, sealed envelopes. 10 of these envelopes will contain the word "Experimental," and the remaining 10 will contain the word "Control." On Day 0 of the study period, each participant will choose an envelope at random, and be assigned to that arm. This technique will ensure that the ratio between patients in each arm is 1:1.

To minimize bias, the outcomes assessor, who is an advanced practice physiotherapist clubfoot provider, will be independent of the study and design teams and blinded, so they will not know which bar has been assigned to which patient.

To ensure that the outcomes assessor remains blinded, a member of the study team will check in the patient at the beginning of each visit, remind the patient and parent about the blinding, and ensure that the bar is removed and hidden from view before the outcome assessor enters the evaluation room.

Unblinding may occur for any participant who has experienced an adverse event, such as clubfoot recurrence, and must return to their original SB, if not already using it. Unblinding will occur for all participants if any severe adverse event occurs that is related to the use of the DB. For unblinding to occur, the outcomes assessor must notify a member of the study team, and any member of the study team may unblind the outcomes assessor.

All intentional and unintentional breaking of the blind will be documented in the study's enrollment log, along with the reason(s) for unblinding. Per protocol, the Data Safety Monitoring Board and Research Ethics Board will also be notified of any adverse events or unblinding.

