4.2 SCIENTIFIC RATIONALE FOR STUDY DESIGN

This trial design allows for direct comparison between SBs and the new DB, without affecting the patient's long-term treatment plan or outcomes. The assessments will be between patients (control vs. experimental cohorts) and within the same patient (experimental cohort wearing both bar designs).

Since participants in this feasibility trial will only use the DB for a maximum of 1 month, the likelihood of finding a difference in bar effectiveness is quite low. Therefore, following this feasibility trial, the study team plans to conduct a prospective randomized controlled trial of the novel DB versus standard bars, comparing the DB's effectiveness at maintaining ideal foot position and preventing recurrence over a minimum two-year period. A separate REB application will be filed for this trial.

Bias in brace wear reporting will also be mitigated in this feasibility study by using temperature sensors to objectively measure the time of brace wear, and by using quantitative evaluations done by blinded outcomes assessors to evaluate study endpoints.

To mitigate the risk of bias in the completion of the parent-reported surveys, the surveys were written using neutral language as much as possible. For example, instead of using the terms "standard" and "dynamic," the bar types were described using the terms "current," "original," and "alternative."

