8.2.4 CLASSIFICATION OF AN ADVERSE EVENT

8.2.4.1 SEVERITY OF EVENT

The severity of an AE will be assessed by a blinded outcomes assessor, physiotherapist [name], and/or the PI. They will use the following definitions when assessing the intensity of an AE:

- Mild Events require minimal or no treatment and do not interfere with the participant's daily activities.
- **Moderate** Events result in a low level of inconvenience or concern with the therapeutic measures. Moderate events may cause some interference with functioning.

• Severe – Events interrupt a participant's usual daily activity and may require systemic drug therapy or other treatment. Severe events are usually potentially life-threatening or incapacitating. Of note, the term "severe" does not necessarily equate to "serious".

The only "severe" AE that is foreseen to potentially occur during the study is clubfoot recurrence. Clubfoot recurrence would likely be treated by serial casting, as is standard care for clubfoot treatment. Mild to moderate AEs may potentially include pressure sores, skin rashes, and unintentional selfinjuries. All of these AEs are known risks associated with FABs.

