8.2.4.2 RELATIONSHIP TO DYNAMIC BAR OR STANDARD BAR

All Adverse Events (AEs) will have their relationship to the DB or SB assessed by the blinded outcomes assessor, physiotherapist [name], and/or the PI, based on temporal relationship and their clinical judgment. The degree of certainty about causality will be graded using the categories below.

- **Definitely Related** There is clear evidence to suggest a causal relationship, and other possible contributing factors can be ruled out. The clinical event occurs in a plausible time relationship to study intervention administration and cannot be explained by concurrent disease or other drugs or chemicals. The response to withdrawal of the study intervention should be clinically plausible.
- **Probably Related** There is evidence to suggest a causal relationship, and the influence of other factors is unlikely. The clinical event occurs within a reasonable time after administration of the study intervention, is unlikely to be attributed to concurrent disease or other drugs or chemicals, and follows a clinically reasonable response on withdrawal.
- **Possibly Related** There is some evidence to suggest a causal relationship (e.g., the event occurred within a reasonable time after administration of the study intervention). However, other factors may have contributed to the event (e.g., the participant's clinical condition, other concomitant events).
- Unlikely to be related A clinical event whose temporal relationship to study intervention administration makes a causal relationship improbable (e.g., the event did not occur within a reasonable time after administration of the study intervention) and in which other drugs or chemicals or underlying disease provides plausible explanations (e.g., the participant's clinical condition, other concomitant treatments).
- **Unrelated** The AE is completely independent of study intervention administration, and/or evidence exists that the event is definitely related to another etiology.

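### One recurrence graded severe and DB-related would, under section 6.3, unblind the outcomes assessor to every child and leave the later recurrence examinations unblinded

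*Combined protocol and SAP*

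**What the plan says.** Section 6.3 has two steps. The first is discretionary and concerns one child: "Unblinding may occur for any participant who has experienced an adverse event, such as clubfoot recurrence", where that child has to go back to the original SB. The second is trial-wide and worded as an obligation: "Unblinding will occur for all participants if any severe adverse event occurs that is related to the use of the DB". The sentence after these says that the assessor must notify the study team and that any team member may then unblind the assessor. This shows that the assessor is the person who learns the allocation.

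The same section provides for a record and for notification: "All intentional and unintentional breaking of the blind will be documented", and the Data Safety Monitoring Board together with the "Research Ethics Board will also be notified of any adverse events or unblinding".

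On severity, section 8.2.4.1 states that the only severe "AE that is foreseen to potentially occur during the study is clubfoot recurrence". On relatedness, section 8.2.4.2 sets out five grades, from definitely related to unrelated: "The degree of certainty about causality will be graded using the categories below". Section 6.3 does not say which of these grades count as related.

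Section 4.2 counters bias by "using quantitative evaluations done by blinded outcomes assessors to evaluate study endpoints", and section 10.1.6 relies on the same blinded evaluations to mitigate the inventors' conflict of interest. Sections 4.1 and 9.3.3 have all children examined for recurrence at each visit. Under 9.3.3, the null hypothesis is rejected if the DB arm has more than 2 recurrences above the control arm.

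**The concern.** The two steps in 6.3 form an escalation and do not contradict each other. The difficulty is the reach of the second. The one severe event the protocol foresees is also the clinical endpoint that the assessor is blinded to judge. A single case with the qualifying grades would show the assessor the arm of every enrolled child.

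Recurrence rests partly on examiner-dependent signs: foot shape, and a 5-degree change in passive dorsiflexion since the previous visit. An assessor who has just seen a relapse attributed to the DB, and who now knows the arms, might look harder at DB children or might become more cautious about calling further cases. Later calls could move in either direction. This would happen just after a failure of the device, when the safeguard in 4.2 and 10.1.6 matters most. The plan names no replacement blinded assessor and does not say how recurrence findings made after unblinding will be handled.

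The rule is also incomplete. The relatedness threshold is undefined, and it is unclear whether children who draw an envelope after the event are covered.

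**Working it through.** The plan gives no figure on this point, so there is none to reproduce. The check has three parts.

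**1. Does one recurrence meet the trigger?**
- The trigger in 6.3 is one adverse event that is severe and related to the DB.
- Section 8.2.4.1 makes recurrence the only severe event foreseen. Section 8.2.3 anticipates an increased recurrence risk with the DB.
- A DB-arm recurrence graded severe and related therefore meets the trigger as written. A control-arm recurrence, or one judged unrelated or not severe, does not. Examinations already done stay blinded.

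**2. How likely is it?** Input: 10 DB children (section 4.1). The documents give no 90-day recurrence risk *p*, so 2%, 5% and 10% are assumptions.

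- At least one DB recurrence: P = 1 − (1 − *p*)^10.
- At least three, the fewest that can satisfy 9.3.3 (more than 2 above a control count of zero): the upper tail of Binomial(10, *p*).
- As a sensitivity, if only half of recurrences qualify as DB-related: 1 − (1 − *p*/2)^10.

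| Assumed *p* | At least 1 | At least 1, half related | At least 3 |
|---|---|---|---|
| 2% | 18.3% | 9.6% | 0.1% |
| 5% | 40.1% | 22.4% | 1.2% |
| 10% | 65.1% | 40.1% | 7.0% |

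The second column is an upper bound on the trigger through recurrence, because it counts every DB recurrence as severe and related. Over this range, a first recurrence is far more likely than the three that 9.3.3 needs.

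**3. How many examinations would lose the blind?** Inputs: 20 children, recruitment of about 2 months (section 4.3), and post-baseline visits at Days 7, 30 and 90 (section 1.3), giving 20 × 3 = 60 examinations. Assumptions: one child enrols every 3 days (study days 0, 3, …, 57), and the study is not suspended. For a trigger at a given child's visit, the count is of examinations dated later in children enrolled by that date. Children not yet randomised are left out, because 6.3 has no allocation to reveal until "each participant will choose an envelope at random, and be assigned to that arm".

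| Trigger at that child's | Later examinations, all randomised children | Excluding the affected child |
|---|---|---|
| Day 7 | 8 to 32 | 6 to 30 |
| Day 30 | 20 to 33 | 19 to 32 |
| Day 90 | 0 to 19 | 0 to 19 |

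Worked case for Day 30:
- Child 1 triggers on study day 30, when 11 children are enrolled. Still to come are 3 Day 7, 10 Day 30 and 11 Day 90 examinations, 24 in all.
- Child 10 triggers on study day 57, when all 20 are enrolled: 3 + 10 + 20 = 33, the maximum (33/60 = 55%).
- Child 20 triggers on study day 87: only the 20 Day 90 examinations remain, the minimum (20/60 = 33%).

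The last column is the excess due to the all-participant rule, since the individual rule already allows the affected child to be unblinded. With one child every 2 or 4 days, the Day 30 range for all randomised children is 20 to 39 or 15 to 29.

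**The case against.** The strongest objection concerns the trigger. Section 6.3 uses recurrence as its example for the individual, discretionary step, and the all-participant sentence does not mention it. Foreseeing recurrence as the only severe event does not mean that every recurrence will be graded severe; 8.2.4.1 also describes severe events as usually life-threatening or incapacitating. It is therefore open which step a DB-arm recurrence falls under. This stands as an ambiguity, and it is why the point is conditional on the grading. It does not remove the route: a case with both grades meets the wording.

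Second, 6.3 requires the assessor to notify the team, and a team member then "may" unblind. This sets out who acts. It is softer language, but it does not cancel the preceding obligation.

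Third, the recurrence risks are assumed, and the counts depend on even accrual and no suspension. Section 10.1.1 allows suspension for unacceptable risk, which such an event might prompt, but this is discretionary. Many of the counted examinations are also at Day 90, when DB children are scheduled to be back on the SB (20 of the 33 in the largest Day 30 case). Knowing the past allocation could still influence those calls.

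Fourth, a trial-wide code break may be a deliberate safety choice for a prototype. However, 6.3 has the study team check children in and hide the bar, so the team already knows each child's bar. Adverse events also go to the DSMB and REB. Neither managing the affected child nor reviewing the arms requires the assessor to know the other children's allocation.

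Finally, the consequence is modest. Recurrence is secondary, the analysis is descriptive, and 9.3.3 disclaims proof of safety or efficacy. This stands and limits the weight of the point.

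**Conclusion.** The concern holds. As written, one DB-arm recurrence graded severe and related obliges the team to unblind the assessor to all participants, and the later recurrence examinations lose the protection that 4.2 and 10.1.6 rely on. At assumed 90-day risks of 2% to 10%, the chance of at least one DB recurrence is 18% to 65%, an upper bound on the trigger by this route. With one child every 3 days and no suspension, a Day 30 trigger would expose 19 to 32 examinations in children other than the affected one. The direction of any bias cannot be predicted. The feasibility conclusions on recruitment and retention are not affected, and sensor-measured wear does not depend on the assessor. This change should be made because it is cheap; it is not a flaw that undermines the trial.

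**What to change.** In section 6.3:
- Limit unblinding of the outcomes assessor to the affected child, and only after that visit's examination and adverse event grades are recorded. Keep the assessor blinded to all other children.
- Leave arm-level safety review to the DSMB, which 6.3 already notifies.
- If an all-participant rule is kept, state whether recurrence falls under it, which of the relatedness grades in 8.2.4.2 trigger it, and whether children randomised later are covered.

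In section 9.3.3, add one line: report recurrences assessed before and after any break of blind separately, using the log that 6.3 already requires.

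The cost is wording in 6.3 and one reporting line in 9.3.3. No staff are added, because the study team already knows each child's bar. The downside is that section 10.1.4 plans a single DSMB meeting, so the charter must provide for event notifications outside it. The proposal changes only what the assessor is told and leaves the clinical management of an affected child as it is.

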6.4 STUDY INTERVENTION COMPLIANCE

Standard care for clubfoot treatment is to assess bracing compliance by asking the parent about the patient's daily wear time at each scheduled appointment. Studies have shown that parents over-report brace wear by approximately 30% (12). To objectively measure brace compliance, a temperature sensor will be added in each patient's boots during the 90-day study period. Measurements obtained from these sensors will be used in the analysis of the 2nd secondary endpoint to compare brace wear time in the SB versus the DB. We will compare these results with parent self-reported logs of brace wear.

The temperature sensors that will be used are the DS1921G-F5 Thermochron iButtons, designed and manufactured by iButtonLink Technology in Wisconsin, USA. Each device is a battery powered data logger equipped with a temperature sensor. The devices will be set to record the temperature of the boots' insoles every 45 minutes and launched on Day 0 and Day 30 on the study period. The device complies with medical standards and is calibrated against a National Institute of Standards and Technology (NIST) traceable source (18). Thermochron iButtons have previously been used in a similar clubfoot bracing adherence study (19). The data obtained from these temperature sensors will be used to calculate the daily brace wear time of each patient during the interventions, by measuring the temperature increase when the child is in the brace.

For unilateral clubfoot cases, the temperature sensor will be placed in the boot that holds the clubfoot. For bilateral cases, the sensor will be placed on the right boot. To implant each sensor, technicians at SickKids will drill a hole through the sole of the boot and insert the iButton with an interference fit. This hole will be located directly over top of the slider in the "Quick Clip" mechanism, so that the slider secures the sensor and prevents it from falling out. The insole of the boot will be then covered with a layer of ShearBan[®] in order to ensure patient comfort and to ensure that the temperature sensor never comes into contact with skin. ShearBan is a self-adhesive film often used in insoles and orthopaedic braces (20). This procedure mimics that of another clubfoot brace compliance study, for which an installation video has been created (21).

The orthotics department will ensure that implantation of the iButton does not compromise the fit or function of the boots. Depending on the size and model of the participant's current boots, each participant will either receive a new boot that is pre-fitted with an iButton sensor, or the iButton sensor will be inserted into their current boot on Day 0 of the study period. If a new boot was given, the study team will collect this boot on Day 90 of the study period, and the participant will return to their original boot. If the iButton sensors are reused for different participants in the study, each sensor will be cleaned with alcohol wipes in between patients as advised by the Infection Prevention and Control department at SickKids.

To launch and retrieve data from the temperature sensors, a member of the study team will have to briefly remove the sensor from the boot on Day 0, Day 30, and Day 90 of the study period. When reinserting the sensor, the research team will ensure that the hole is re-covered with a layer of ShearBan.

If the participant is using their original boots and the parent wishes to remove the sensor after the study is complete, the research team will remove the sensor and cover the hole with a layer of ShearBan.

7 DISCONTINUATION AND WITHDRAWAL

7.1 DISCONTINUATION OF STUDY INTERVENTION

Early discontinuation from either FAB bar does not mean discontinuation from the study, and remaining study procedures should be completed as indicated by the study protocol. If a clinically significant finding is identified after enrollment, the PI or qualified designee will determine if any change in participant management is needed. Any new clinically relevant finding will be reported as an Adverse Event (AE).

7.2 PARTICIPANT DISCONTINUATION/ WITHDRAWAL FROM THE STUDY

Participants are free to withdraw from participation in the study at any time upon request. An Investigator may discontinue or withdraw a participant from the study for the following reasons:

- Withdrawal of informed consent (participant or parent/guardian withdraw for any reason)
- If any clinical Adverse Event (AE), laboratory abnormality, or other medical condition or situation occurs such that continued participation in the study would not be in the best interest of the participant.
- If the participant meets an exclusion criterion (either newly developed or not previously recognized) that precludes further study participation.

The reason for participant discontinuation or withdrawal from the study will be recorded in the study enrollment log. Patients who do not follow the prescribed bracing schedule will still be included in the study and recorded with the intention to treat principle. Similarly, if the DB prototype breaks or malfunctions and cannot be quickly repaired, the patient will return to their original SB but will not be withdrawn from the study.

Participants who sign the informed consent form, but do not return for study visits 1, 2 and/or 3 will be replaced. Participants who sign the informed consent form, and return for study visits 1, 2 and 3 but subsequently withdraw, or are withdrawn or discontinued from the study will not be replaced. The data from participants who are withdrawn or discontinued from the study will be used in the analysis unless the participant requests otherwise.

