1.2 SCHEMA

1.3 SCHEDULE OF ACTIVITIES (SOA)

Procedures	Screening Day -30 to -1	Baseline, Visit 1 Day 0	Study Visit 2 Day 7+/- 3 days	Study Visit 3 Day 30 +/-7 days	Study Visit 4 Day 90 +/- 7 days
Chart Review for screening	Х				
Measure patients for appropriate size of SB and DB		Х			
Informed consent		Х			
Complete Consent Discussion Form		Х			
Randomization		Х			
Prescribe study intervention (new DB or original SB)		Х			
Launch/retrieve data from temperature sensor in boot		х		х	х
Physical exam		Х	Х	Х	Х
Adverse event review			Х	Х	Х
Administer surveys		Х		Х	Х
Video record patients in their prescribed bar				х	

Procedures	Screening Day -30 to -1	Baseline, Visit 1 Day 0	Study Visit 2 Day 7 +/- 3 days	Study Visit 3 Day 30 +/-7 days	Study Visit 4 Day 90 +/- 7 days
Distribute/collect brace wear log		Х		Х	Х
Document on study enrollment log	Х	Х	Х	Х	Х

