4 STUDY DESIGN

4.1 OVERALL DESIGN

This is an assessor-blinded randomized controlled trial in which patients with well-corrected idiopathic clubfoot will be randomized to wear either their original SB (which is standard care for clubfoot treatment) or the new DB for 30 days. After 30 days, all participants will resume use of the SB and be monitored for an additional 60 days.

This study is a "feasibility trial" as it is assessing the feasibility of conducting a large-scale randomized controlled trial to evaluate the effectiveness of the DB. As such, feasibility will be determined by the ability to recruit patients within the goal study period and to retain participants.

On Day 0 of the study period, patients will be randomized and receive baseline clinical and questionnaire evaluations. A temperature sensor will be added in each participant's boots during the 90-day study period to objectively measure time of brace wear.

All patients will be evaluated after 7 days in their assigned bar to check for brace fit, any complications, and to perform required adjustments. This 7-day checkup is standard care for clubfoot treatment when patients receive the SB and FAB for the first time.

After 30 days, the patients wearing the DB will resume use of the SB. All patients will be seen at the end of the first 30 days and after 90 days to monitor for recurrence of the clubfoot deformity, complications of brace wearing, and parent-reported perception of their child's comfort with the FAB. Parents will also be asked to complete a self-reported brace wear log that will be collected on Day 30 and 90.

A minimum of 10 patients per arm will be recruited. Once there are 10 in each arm, recruitment will halt. It is hypothesized that patients using the DB will experience higher brace tolerance as measured by the temperature sensors, and higher comfort levels as reported by parents, without an increase in clubfoot deformity recurrence compared to the SB.

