4.3 END OF STUDY DEFINITION

A participant is considered to have completed the study if he or she has completed all phases of the study including the last visit or the last scheduled procedure shown in Section 1.3, Schedule of Activities (SoA). The duration of participation for each individual participant who completes all study visits will be 3 months.

The end of the study is defined as completion of the last visit or procedure shown in the SoA in the trial globally. It is estimated that it will take 5 months from when the study opens to enrollment until the end of the study, as patient recruitment is expected to take approximately 2 months.

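### Section 7.2 replaces children who have already drawn one of the 20 envelopes, and the plan supplies no random allocation for entrants after the 20th draw

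*Combined protocol and SAP*

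**What the plan says.** All references are to the combined protocol and SAP.

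- **Timing of the draw.** The schedule of activities (1.3) places consent and randomisation at "Baseline, Visit 1 Day 0". Visit 2 is Day 7 and Visit 3 is Day 30.
- **Allocation (6.3).** "This will be done by preparing 20 opaque, sealed envelopes", ten for each arm. Then: "On Day 0 of the study period, each participant will choose an envelope at random, and be assigned to that arm". The section concludes: "This technique will ensure that the ratio between patients in each arm is 1:1".
- **Replacement (7.2).** "Participants who sign the informed consent form, but do not return for study visits 1, 2 and/or 3 will be replaced". A child who attends Visits 1 to 3 and leaves later is not replaced.
- **Stopping recruitment (4.1).** Ten per arm is called a minimum, and then: "Once there are 10 in each arm, recruitment will halt".
- **Who knows the arms (6.3).** Only the outcomes assessor is blinded, and "any member of the study team may unblind the outcomes assessor", so the team holds the assignments.
- **Counting (4.3, 9.1, 9.2, 9.3.2).** Completion is defined: "A participant is considered to have completed the study if he or she has completed all phases of the study including the last visit". The intent-to-treat (ITT) and arm populations are all registered children, and dropout is to be described in them. Section 9.1 forecasts the time needed to register 20 participants.

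No section mentions spare envelopes, resealing a used one, or the arm that a replacement enters.

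**The concern.** The number of envelopes fits the planned 20 children with none to spare, while 7.2 allows more than 20 children to be allocated. Once a 21st child is needed, the plan does not say how that child gets an arm. The team must then improvise, and the targets it would be trying to meet (10 per arm, 1:1) lead naturally to the arm that lost a child. An assignment chosen that way is known before the family is approached. The people who know it include investigators with a declared interest in the dynamic bar (DB) (10.1.6).

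At stake is whether the random allocation described in 6.3 covers every child, in a trial that rehearses a larger randomised trial. Retention is part of the primary objective, so it should also be clear that a replaced child remains in the dropout count.

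**Working it through.** **1. Reproduce the plan's count.** Envelopes: 10 + 10 = 20 (6.3). Planned children: 2 × 10 = 20 (4.1). These match exactly, leaving 0 spare.

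**2. Which replacements use an envelope.** A child who never attends Visit 1 has drawn nothing and causes no shortfall. A child who misses Visit 2 or 3 drew on Day 0. Let k be the number replaced for that reason:

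- allocations needed = 20 + k; envelopes = 20; shortfall = k
- share of entrants without an envelope = k/(20 + k): 1/21 = 5%, 2/22 = 9%, 4/24 = 17% for k = 1, 2, 4

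A replacement who enters before the 20th draw still draws at random. The shortfall falls on the last k entrants, whoever they are.

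**3. How likely k ≥ 1 is.** The documents give no loss rate. Let p be the assumed chance that a child who has drawn misses Visit 2 or 3, independent between children.

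- P(at least one among the first 20) = 1 − (1 − p)^20
- expected extra entrants, if replacement continues until 20 have attended through Day 30 = 20p/(1 − p)

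| Assumed p | P(at least one) | Expected extra entrants |
|---|---|---|
| 1% | 18% | 0.2 |
| 2% | 33% | 0.4 |
| 5% | 64% | 1.1 |
| 10% | 88% | 2.2 |
| 20% | 99% | 5.0 |

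**4. When the need would appear.** Assume the 20 draws are spread evenly over the planned 2 months, at days 60i/19 for i = 0 to 19. Day 30 falls after the last draw when 60i/19 + 30 > 60, that is i ≥ 10, which is 10 of the 20 children. A replacement can therefore fall due when the envelopes are used up and recruitment has halted.

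**5. Can an unwritten workaround close the gap?**

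- *Placing the child in the vacated arm:* the assignment is known in advance.
- *Resealing the used envelope after the other 19 are gone:* the pool holds one envelope, so the result is again known.
- *One fresh 50:50 draw after one loss:* random, but it restores 10:10 only 50% of the time, so the ratio in 6.3 is no longer ensured among the children who stay.

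**6. Comparison with the original pool.** In a random order of 10 + 10, the expected number of draws left after one arm is exhausted is 2 × 10/11 = 1.8. The team can deduce those assignments too.

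**The case against.** The strongest reply is that this is silence and not contradiction. Section 6.3 prepares 20 envelopes for 20 planned children and does not forbid more. Ten per arm is a minimum, and the halt in 4.1 can be read as not counting replaced children. That stands in part: the rules would fit if further envelopes were sealed. But nothing tells the team to do so, and the 10-per-arm and 1:1 statements pull the other way.

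Three further points stand:

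- **Predictability is not new.** About 1.8 of the original 20 draws are already deducible, close to the 2.2 extra entrants expected at 10% loss. The first 20 allocations are not fully concealed either.
- **Loss may be low.** Each extra visit is compensated, with payment at the final visit (5.4). Missed visits are rescheduled and contact is repeated (7.3). Stopping a bar is not leaving the study (7.1). This does not establish a low rate, but it is why the range above starts at 1%.
- **Dropout counting is largely in place.** Read literally, the registered populations in 9.2 keep replaced children in, and 4.3 and 7.3 largely define completion and loss. What remains is that registered is not tied to randomisation. The 20 in 9.1 is a forecast and defines no population.

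A reader might infer that the plan abandons concealment or prescribes a biased allocation for replacements. The documents do not support that: no section directs a child to a named arm. Nor do they support the inference that replacement removes early dropouts from the primary endpoint.

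**Conclusion.** The point holds as a gap between 7.2, 6.3 and 4.1: the plan provides 20 random allocations and a replacement rule that can require 20 + k. It supplies no allocation method for the last k entrants. The count needs no assumption. How likely the gap is to matter does: 18% to 99% for an assumed early loss of 1% to 20%, with 0.2 to 5.0 extra entrants expected.

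The consequence is small. The analysis is descriptive (9.3.1), and the recurrence comparison is not meant to prove safety or efficacy (9.3.3). The effect is confined to how a few children are allocated and to a clear dropout denominator. It should still be fixed before recruitment, because it is likely to arise at moderate loss and the correction is cheap.

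**What to change.** **Preferred: amend 7.2.** Replace a child only if no envelope has been opened for that child. Children who have drawn are not replaced, stay in the ITT population, and count as dropouts if they do not complete Day 90. The cost is a few words. The downside is that an arm may have fewer than 10 children reaching Day 30. At assumed early loss of 5%, 10% or 20%, both arms keep all 10 with probability (1 − p)^20 = 36%, 12% or 1%. Both keep at least 8 with probability [P(Bin(10, p) ≤ 2)]² = 98%, 86% or 46%.

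**Alternative: amend 6.3 and 4.1.** Seal a small balanced reserve in advance, for example 4 + 4. Each child after the 20th draws from it at random, and none is placed in a named arm. Recruitment then halts at a stated total: 20 plus one per replaced child, at most 28. Downsides:

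- Ten per arm reaching Day 30 is not guaranteed. One free draw restores the lost arm in 50% of cases. Four draws restore a 2:2, 3:1 or 4:0 loss in 36/70 = 51%, 16/70 = 23% or 1/70 = 1%.
- A reserve of 8 is exhausted (more than 8 extra entrants needed) in under 0.1%, 0.1% or 9% of trials at 5%, 10% or 20% loss.
- Section 6.1 has each DB prototype used on two patients, which implies 10/2 = 5 prototypes. Up to 14 DB allocations would imply 7, or reuse beyond that statement, so supply must be reconciled with 6.1. Sensor-fitted boots and recruitment time are also affected.
- The end of the reserve is predictable, like the end of the original pool.

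**Under either (9.2 and 9.3.2).** Define ITT as all randomised children, and state that the dropout denominator is all randomised children, including any who were replaced, overall and by arm. A child who misses only Visit 2 but completes Day 90 should be addressed explicitly. Exact confidence intervals are optional.
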